4.3 Baseline Definition

For all variables, baseline will be considered to be the last value obtained prior to first start of treatment, and may be on Screening or on Day 1, dependent on parameter. Change from baseline will be the difference between the value at a given time point and the baseline value.

4.4 Definition of Study Day and Visit Window

4.4.1 Study Day

For each patient, the day of first dose of study medication (Nanocort/placebo IV infusion and Depo-Medrol/placebo IM injection) administered on or after the day of randomization will be considered study day 1. Each assessment will be assigned a study day. The calculation for study day is dependent on whether the actual date of assessment is before or after the date of study day 1 and is calculated as follows:

Before study day 1: study day = (date of assessment – date of study day 1).

On or after study day 1: study day = (date of assessment – date of study day 1) +1.

If the full date of the assessment is not known or not imputable based on the guidelines in Section 4.2, then no study day will be assigned.

For each patient, the end of the study is defined as the date of their last contact in this study.

4.4.2 Visit Window

Data will be analyzed based on the categorized visit captured in the database. No dates will be used to reassign visits or define visit windows. The visits captured in the database include:

4.5 Patient Disposition

The number and percentage of subjects allocated to each of the populations will be summarized for all enrolled subjects. The number and percentage of subjects completing the study, discontinued, the reasons of discontinuation and the study duration (end of study date-date of first treatment +1) will be tabulated overall and by treatment.

4.6 Demographics and Baseline Characteristics

Subject demographics and baseline characteristics, including date of birth, race, height, smoking history and Rheumatoid Factor (RF) will be summarized by treatment group and overall.

4.7 Medical and Surgical History

Numbers and percentages of subjects with any known history of relevant abnormalities, disease or surgery will be summarized by treatment group and overall. Reported term, preferred term, body system code, date of onset/procedure and date of resolution or ongoing will be listed.

Medical history will be coded by the MedDRA coding dictionary, version 19.

4.8 Efficacy Analysis

The primary and key secondary analyses will be completed for the ITT and PP populations.

Due to early termination of the study, the sample size will be much less than planned. As a result, the statistical power can be inadequate for the planned gatekeeping methodology. Therefore, standard hypothesis testing methods may be used instead to analyze the data.

[figure not shown]
To account for these possibilities and to facilitate better understanding of the data, the data will be analyzed 'as planned' in the protocol AND using more simple, unadjusted alpha analyses with basic chi-square tests. Therefore the data (Table 8A and 8B) will be analyzed two ways:

- Original Primary and Key Secondary Analyses using Hochberg's procedure and gatekeeping methods
- Modified Primary and Key Secondary Analyses using simple chi-square tests.

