4.4 Sample size calculation

A total of 330 subjects will be enrolled and randomized into 3 groups of 110 subjects.

The EULAR response will be considered as primary parameter.

There is a special interest in the percentage of subjects with an EULAR response category of good or moderate (good and moderate combined) and the percentage of subjects with an EULAR response category of only good. These subjects will be called **EULAR responders** and **EULAR good-responders**, respectively.

Primary endpoint:

- the percentage of EULAR responders (good and moderate combined) at Day 8

Key secondary endpoints:

[figure not shown]
- The percentage of EULAR good-responders at Day 8
- The percentage of EULAR responders at Day 15
- The percentage of EULAR good-responders at Day 15

The sample size calculation for this study is based on group comparisons of EULAR responder rates (Nanocort 150 mg compared to Depo-Medrol® and Nanocort 75 mg compared to Depo-Medrol®) at Day 8. The study is called positive if one of the primary null hypotheses will be rejected.

The following primary null hypotheses will be considered:

$H_{0,1}$: EULAR responder rate at Day 8 for Nanocort 150 mg = EULAR responder rate at Day 8 for Depo-Medrol®

$H_{0,2}$: EULAR responder rate at Day 8 for Nanocort 75 mg = EULAR responder rate at Day 8 for Depo-Medrol®

Taking a drop-out rate of approximately 10% into consideration, a sample size of 110 subjects per treatment arm will be sufficiently large to show superiority of Nanocort compared to Depo-Medrol® in EULAR responders at Day 8 and to assess the safety of Nanocort in this study.

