8.2 Randomisation, blinding and treatment allocation

Subject randomization will take place before the start of administration of the IMP.

Subjects will be randomized in a 1:1:1 ratio to the three treatment arms and stratified by site.

Randomization of the subjects will be performed by an Interactive Web-based Randomization System (IWRS) by an independent party. The randomization number will be recorded on the eCRF. Once the numbers have been assigned they cannot be reassigned.

Subjects in this trial will be randomized in a 1:1:1 ratio to receive one of three dose groups:

- **Nanocort 75 mg** IV infusion and IM saline injection on Day 1 and Day 15, or
- **Nanocort 150 mg** IV infusion and IM saline injection on Day 1 and Day 15, or
- **Depo-Medrol 120 mg** IM injection and IV saline infusion on Day 1 and Day 15

Blinding:

Prior to the start of the study, a copy of the master randomization code will be stored in confidential manner up to the unblinding after database lock. A separate unblinded Pharmacovigilance Medical Reviewer and unblinded Pharmacovigilance Associate will be available for triage, review and submission of safety events.

Any reported Suspected Unexpected Serious Adverse Reactions (SUSARs) will be triaged by the Medical Monitor in a blinded fashion and forwarded for full processing to the unblinded Medical Reviewer and unblinded Pharmacovigilance Reviewer for processing and reporting to the Competent Authority (CA) and Independent Ethics Committee (IEC) per regulations.

Unblinding to Investigator and subject will occur only after database closure at the end of the study. The study blind will only be broken after database lock except in the case of

emergency to protect subject's safety. The code may be broken in case of an emergency, preferably after discussion with the MM. Any code break will be recorded and a copy retained within the study file.

The blind will be preserved throughout the study unless, in the opinion of the Investigator, the lack of this information places the subject at undue risk. In general, this will occur only if an adverse event occurs for which the subject's physician requires knowledge of the treatment assigned. In this case, the Sponsor should be notified as soon as possible and un-blinded information for the subject's treatment group will be provided.

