10.2 Primary study parameter

EULAR responders (good and moderate combined) at Day 8

EULAR responders (good and moderate combined) at Day 8 will be summarized by treatment group and pair-wise compared between both Nanocort arms and the Depo-Medrol arm using the Cochrane-Mantel-Haenszel test stratified by study site.

As sensitivity analysis a logistic regression model will be fitted on the EULAR responders with the stratification factor study site and additional baseline variables as covariates.. Proportional odds ratios will be presented. The SAP will specify the planned additional covariates .

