4.8.1.2 Key Secondary Analyses

The three key secondary endpoints are: 1) EULAR response (good) rate at Day 8, 2) EULAR response (good and moderate combined) rate at Day 15, and 3) EULAR response (good) rate at Day 15. Both comparisons (Nanocort 150 mg vs. Depo-Medrol[®], and Nanocort 75 mg vs. Depo-Medrol[®]) will be completed for each of the three key secondary endpoints (i.e., up to 6 key secondary analyses).

The key secondary hypotheses will only be tested if at least one primary analysis is significant. If for one of the dosages the primary analyses is not significant, then the corresponding key secondary hypotheses will not be tested. The key secondary hypotheses will be tested with a two-sided confidence level, α_s . The calculation of α_s depends on the maximum p-value from the primary hypotheses, the significance of the primary hypotheses and α_p .

Step 1: The primary hypotheses are tested using Hochberg procedure at $\alpha_p = 0.045 < \alpha$ (0.05). If at least one of the primary null hypotheses is rejected then go to Step 2. The significance value for Step 2 (α_s) is a function of largest primary p-value.

Step 2: Test the secondary null hypotheses using Hochberg procedure at α_s .

$$\begin{aligned}\alpha_s &= \min(\lambda \alpha^*/(p^*)^2, \alpha_p) && \text{if } p^* > \alpha_p \text{ and} \\ \alpha_s &= \alpha && \text{if } p^* \leq \alpha_p\end{aligned}$$

[figure not shown]
Where p^* is the largest primary p-value, λ is chosen to control the global FWER at the alpha level.

$$\begin{aligned}\alpha^* &= \alpha_p(1 - \sqrt{2 - \alpha_p/(k_1 - 1)} - \alpha / \alpha_p)^2 && \text{if } \alpha' \leq \alpha \\ &= \alpha_p(\alpha - \alpha_p) / (k_1 - 1 - \alpha_p) && \text{if } \alpha' > \alpha\end{aligned}$$

Where $\alpha' = \alpha_p + \alpha_p^2 / (k_1 - 1) - \alpha_p^3 / (k_1 - 1)^2$

K_1 = Number of primary endpoints (in this case $k_1 = 2$)

The significance level carried over to α_s depends on the magnitude of the primary p-values rather than the number of significant primary p-values. This method assumes a full parametric model. The joint distribution of the hypotheses in primary and secondary endpoints is considered to calculate λ . If the joint distribution of the test statistic is not specified, the λ parameter is chosen under the worst-case scenario.

The key secondary analyses will be completed for the ITT and PP populations.

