4.11 Modifications from the statistical section in the protocol

The protocol stated hypotheses with one-sided testing using less than and greater than symbols. This is corrected in the SAP to two-sided hypotheses, as planned, using equal and not equal symbols.

The protocol stated that Cochrane-Mantel-Haenszel test stratified by study site will be used for the primary analysis. However, this conflicts with the primary and key secondary hypotheses planned in the protocol which are not stratified, so this is revised in the SAP to match with the planned hypotheses.

Due to early termination of the study, the sample size will be much less than planned. As a result, the statistical power can be inadequate for the planned

gatekeeping methodology. Therefore, standard hypothesis testing methods may be used instead to analyze the data (see section 4.8).

5. Interim analyses

No interim analyses were planned.

6. Sample size and Power calculations

A total of 330 subjects were to be enrolled and randomized into 3 groups (1:1:1).

The EULAR response rate will be considered as primary parameter. See Appendix B for details on scoring and coding. There is a special interest in the percentage of subjects with an EULAR response category of good or moderate (good and moderate combined) and the percentage of subjects with an EULAR response category of only good. These subjects will be called EULAR responders and EULAR good-responders, respectively.

[figure not shown]

Primary endpoint:

- The percentage of EULAR responders (good + moderate) at Day 8

Key secondary endpoints:

- The percentage of EULAR good responders at Day 8
- The percentage of EULAR responders at Day 15
- The percentage of EULAR good responders at Day 15

[REDACTED]

[REDACTED]
[REDACTED]
[REDACTED]
[REDACTED]
[REDACTED]
[REDACTED]

The sample size calculation is based on estimates from [REDACTED]

[REDACTED]
[REDACTED]
[REDACTED]
[REDACTED]
[REDACTED]
[REDACTED]
[REDACTED]
[REDACTED]
[REDACTED].

Although the above described the planned sample size, the study enrollment did not reach the planned goal, and the study may likely have inadequate statistical power.

7. Tables, Listings and Figures

Below are the titles for the planned study tables, listings and figures

Table 1	Subject Distribution
Table 2.A	Subject Distribution By Center (ITT)
Table 2.B	Subject Distribution By Center (PP)
Table 3.A	Demographics and Baseline Characteristics (ITT)
Table 3.B	Demographics and Baseline Characteristics (PP)

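### EULAR good response depends on baseline DAS28 by definition, yet the SAP's primary and key secondary tests are unadjusted and it drops, without saying so, the protocol's covariate-adjusted sensitivity model

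*Combined protocol and SAP*

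**What the plan says.** **Endpoints.** The primary endpoint is EULAR good or moderate response at Day 8. SAP 4.8.1.2 begins its list of key secondaries: "The three key secondary endpoints are: 1) EULAR response (good) rate at Day 8". The other two are good or moderate response at Day 15 and good response at Day 15. Two of the three are therefore good response.

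**Definition.** Protocol 8.3 and SAP Appendix B agree. Good response needs a DAS28 of 3.2 or less at the visit and an improvement of more than 1.2. Good or moderate response needs an improvement of more than 1.2, or of more than 0.6 with a visit DAS28 of 5.1 or less.

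**Entry and allocation.** Entry requires a DAS28 of at least 3.2, with no upper limit (protocol 4.2). Protocol 8.2: "Subjects will be randomized in a 1:1:1 ratio to the three treatment arms and stratified by site". Baseline DAS28 is not a stratification factor.

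**Protocol analysis.** Protocol 10.2 compares arms by a Cochran-Mantel-Haenszel test stratified by site. As a sensitivity analysis it adds a logistic regression with site and further baseline covariates, and states: "The SAP will specify the planned additional covariates". Protocol 10.3 analyses the key secondaries in the same way as the primary.

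**SAP analysis.** SAP 4.8 runs the Hochberg and gatekeeping analysis and, beside it, "Modified Primary and Key Secondary Analyses using simple chi-square tests". SAP 4.11 removes the site stratification. No section contains the logistic regression or names covariates for it, and 4.11 does not list the omission, although the opening of SAP section 4 undertakes to document every departure from the protocol. In SAP 4.8.3, baseline DAS28 is a covariate in the HAQ and FACIT models, and the baseline score is one in the DAS28 models. SAP 4.6 does not name it among the baseline characteristics to be summarised.

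**The concern.** A subject who enters at 6.0 must fall by 2.8 to count as a good responder; one who enters at 4.4 needs just over 1.2. A test that ignores this leaves a known source of variation in the comparison. The loss costs more in a trial stopped early: SAP 4.8 says that "the sample size will be much less than planned" and that power may be inadequate. Its response is a simpler unadjusted test, while a predictor already measured in every analysed subject goes unused.

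The second matter is traceability. The one covariate-adjusted analysis of these endpoints that the protocol planned has disappeared without a record. A reader who relies on 4.11 as the full list of departures would not know that it existed.

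**Working it through.** **1. The plan's own figure.** Protocol 4.4: "Taking a drop-out rate of approximately 10% into consideration, a sample size of 110 subjects per treatment arm". This gives 110 × 0.90 = 99 evaluable per arm, and 3 × 110 = 330 in total. The responder rates and power behind it are not available (SAP section 6 stops at "The sample size calculation is based on estimates from" and is then blacked out), so the sample size cannot be reproduced. For scale, at 99 per arm, two-sided 0.045 and 80% power, the detectable difference is about 17 to 20 points for control rates of 0.3 to 0.7.

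**2. Improvement required at baseline b (arithmetic from the definition).**
- Good response: more than 1.2 if b ≤ 4.4; otherwise at least b − 3.2.
- Good or moderate: more than 0.6 if b ≤ 5.7; at least b − 5.1 between 5.7 and 6.3; more than 1.2 from 6.3.

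| Baseline | Good | Good or moderate |
|---|---|---|
| 4.4 | >1.2 | >0.6 |
| 5.0 | 1.8 | >0.6 |
| 6.0 | 2.8 | 0.9 |
| 7.0 | 3.8 | >1.2 |

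The dependence is steep for good response and slight for the primary.

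**3. How much baseline explains (simulated).** Assumed: baseline mean 4.6–5.4, SD 0.8–1.1, cut off below 3.2; mean improvement 1.0–2.0, residual SD 1.0–1.1, slope of improvement on baseline 0–0.5. Baseline explains about 3–26% of the variance of good response (AUC 0.55–0.80) and about 1–7% for good or moderate response (AUC 0.52–0.69). In one mid-range case (mean 5.0, SD 1.1, improvement 1.5, slope 0), good-response rates by baseline quartile were 0.61, 0.48, 0.26 and 0.08.

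**4. Power with and without adjustment.** Two sets of assumptions were used.

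*Set A.* Baseline N(4.8, 1) cut off below 3.2; improvement 0.9 against 1.3, SD 0.9, slope 0–0.4; two-sided 0.0225 (0.045/2, the stricter Hochberg step; SAP 4.8.1.2: "The primary hypotheses are tested using Hochberg procedure at" 0.045).
- At 99 per arm, the chi-square has 36–41% power for good response. A likelihood-ratio test adjusted for baseline (linear and quadratic) has 43–45%. With an adjusted score test matched to the chi-square's size, the gain is about 3.5–7 points.
- At 40 per arm, the chi-square has 14.4% (slope 0) and 15.8% (slope 0.4). The likelihood-ratio test gives 17.1% and 17.3%, but its size is 0.025–0.030 against 0.0225. With size matched, the likelihood-ratio figures fall to 14.4% and 15.5%, which is no gain; the size-matched score test gains about 0.5–2 points.
- For the primary, the size-matched gain is about 0–4 points, mostly 1–2.

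*Set B.* Four scenarios, treatment shift 0.5 DAS28 units, two-sided 0.05, 2,000 trials each, likelihood-ratio test without size matching. Entries are unadjusted → adjusted power.

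| Baseline mean, SD; improvement; slope | Good, 99/arm | Primary, 99/arm | Good, 50/arm |
|---|---|---|---|
| 5.0, 0.8; 1.2; 0.3 | 0.637 → 0.673 | 0.627 → 0.632 | 0.377 → 0.406 |
| 5.0, 1.1; 1.5; 0 | 0.544 → 0.645 | 0.554 → 0.569 | 0.309 → 0.371 |
| 5.4, 1.1; 1.5; 0 | 0.479 → 0.587 | 0.585 → 0.596 | 0.287 → 0.368 |
| 5.0, 1.1; 1.5; 0.5 | 0.758 → 0.778 | 0.570 → 0.607 | 0.468 → 0.481 |

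The good-response gain at 99 per arm runs from 2 to 11 points and is largest when improvement is unrelated to baseline. Monte Carlo error is about √(0.25/2000) = 1.1 points.

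**5. Validity and chance imbalance.** With no treatment effect, the unadjusted chi-square rejected in 0.040–0.059 of trials at nominal 0.05. The adjusted likelihood-ratio test at 30 per arm rejected in 0.052–0.068. A one-SD chance imbalance in mean baseline moves the good-response difference by 1.4–3.2 points at 99 per arm and 1.8–5.6 at 30. For comparison, at an assumed rate of 0.25 the standard error of that difference is √(2 × 0.25 × 0.75/99) = 6.2 points, and 9.7 points at 40 per arm.

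**6. The gate.** SAP 4.8.1.2 tests a dose's key secondaries only if that dose's primary is significant. Requiring both at 0.0225 under set A at 40 per arm, power for good response moves from 6–7% to 7–8%.

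**The case against.** The strongest reply is that nothing is invalid and little is gained. Randomisation already allows for chance imbalance, and the chi-square holds its error rate. In the truncated trial the size-matched gain is a point or two, and after the gate about one. SAP 4.8.3 already plans baseline-adjusted ANCOVA of DAS28 at Weeks 1 and 2, provided the scores look roughly normal, and that uses the continuous measure behind the response. The hypotheses in SAP 4.8.1.1 are plain rate differences. All of this stands, and it limits the point to a cheap improvement.

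It could also be said that SAP 4.8, by promising the analysis as planned in the protocol, carries the logistic model over. That does not hold. SAP 4.8 describes the original analysis only as Hochberg and gatekeeping, no planned table shows a logistic model, and without named covariates it cannot be run as specified.

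Three stronger readings are tempting, and the documents do not support them:
- A reader might infer that baseline nearly settles good response. It sets the hurdle, but under the assumptions tried it leaves about 74–97% of the variance unexplained. Below 4.4 (about 31% of subjects under set A) the hurdle does not change at all.
- A reader might infer that imbalance biases the test. It costs precision; it does not raise type I error.
- A reader might infer that the protocol promised a baseline-adjusted primary test. The covariates left to the SAP belong to a sensitivity model.

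**Conclusion.** The point holds as a modest loss of precision together with an unrecorded departure from the protocol. The departure and the link between good response and baseline follow from the documents alone. The size does not: it rests on assumed DAS28 distributions, on an assumed 40 per arm for the truncated trial (the SAP gives no achieved number), and on power before gatekeeping. On that footing, adjustment is worth about 3 to 7 points for good response at 99 per arm, about 0.5 to 2 at 40 per arm, and little for the primary. It would not rescue an underpowered trial. The main benefit is a planned estimate that accounts for baseline if the arms happen to differ.

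**What to change.** Before unblinding:
- In SAP 4.8, restore the logistic regression for the primary and all key secondary comparisons, with treatment and baseline DAS28 named as covariate. State its functional form; the gains above used linear and quadratic terms. Handle site in whatever way is adopted for the main test, pooling small sites by a rule fixed while blinded.
- Take the p-value from a score, Firth or permutation test. Power was checked here for the score test only.
- Report the baseline-standardised response-rate difference with its confidence interval beside the chi-square result.
- Add baseline DAS28 by arm to the baseline table in SAP 4.6.
- Record in 4.11 how the model now differs from protocol 10.2.

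Making the adjusted model the source of the main p-value is optional and goes beyond what the protocol planned.

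The cost is SAP wording and one extra model. No data need be collected and no analysed subject is lost, because EULAR response cannot be calculated without a baseline DAS28. The one downside is slight small-sample liberality if the likelihood-ratio test is used.

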4.8.1 Original Analyses

4.8.1.1 Primary Analyses

The primary endpoint is EULAR response (good and moderate combined) rate at Day 8. The primary analysis involves two comparisons: 1) Nanocort 150 mg vs. Depo-Medrol[®], 2) Nanocort 75 mg vs. Depo-Medrol[®].

H0,1 : EULAR response (good and moderate combined) rate at Day 8 for Nanocort 150 mg - EULAR responder rate at Day 8 for Depo-Medrol[®] = 0

vs

H1,1 : EULAR response (good and moderate combined) rate at Day 8 for Nanocort 150 mg - EULAR responder rate at Day 8 for Depo-Medrol[®] ≠ 0

and

H0,2 : EULAR response (good and moderate combined) rate at Day 8 for Nanocort 75 mg - EULAR responder rate at Day 8 for Depo-Medrol[®] = 0

[figure not shown]
vs

H1,2 : EULAR response (good and moderate combined) rate at Day 8 for Nanocort 75 mg - EULAR responder rate at Day 8 for Depo-Medrol[®] ≠ 0

The primary analyses will be completed for the ITT and PP populations.

